Title Page

Title: Safety Education in the Emergency Department: A Pilot Study

Identifier: NCT05168878

Document date: April 17, 2020

COMIRB Protocol

COLORADO MULTIPLE INSTITUTIONAL REVIEW BOARD

[name] [contact] [contact]

Protocol #: 20-0238

Project Title: Safety Education in the Emergency Department (SEED): A pilot study

Principal Investigator: [name]

Version Date: 04/17/2020

I. Hypothesis and specific aims

The goal of this proposal is to determine the feasibility and acceptability of using a video in the Emergency Department (ED) at the Children's Hospital Colorado (CHCO) to promote the safe storage of firearms, and safe firearm behaviors, in homes with children. We also intend to obtain pilot data to evaluate parental storage practices and knowledge surrounding temporary firearm transfer out of the home in times of crisis and determine whether these can be improved following a standardized ED intervention. Our overall hypothesis is that presenting a video during a child's ED stay will improve communication with the ED provider ultimately increasing safe firearm storage. In order to test this hypothesis, we are proposing a pilot study to test the feasibility, acceptability and effectiveness of a video intervention in the ED with the following aims:

Aim 1: Aim 1: Evaluate the effectiveness of safe firearm storage education for medical and surgical patients in the Children's Hospital Colorado (CHCO) ED by measuring change in self-reported safe storage at baseline and 3 months after a brief ED intervention.

Hypothesis: Safe storage counselling will improve safe storage practices by 15% over baseline rates, as measured by removing all guns from home or locking all guns and locking ammunition separately.

Aim 2: Evaluate the effectiveness of a brief ED intervention in improving parental knowledge surrounding temporary firearm transfer out of the home as a lethal means restriction strategy by measuring parental knowledge at baseline and 3 months after a brief ED intervention.

Hypothesis: Parents will not be aware of temporary firearm storage as a lethal means restriction strategy, and an ED intervention will be effective at improving this knowledge.

Aim 3: Compare the feasibility of having parents watch a short, 30-second, to a long, 3-minute, Be SMART firearm safety video in the CHCO ED.

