This will be an experimental pre-post pilot study performed in the ED at CHCO. Patients presenting to the ED with a non-emergent complaint will be screened by PRAs or the Principal Investigator and approached to participate after they are assigned an ED room and prior to leaving the room due to discharge, transfer or admission. Since this study is observational in nature, participation will not alter medical treatment or length of stay in the ED; therefore, after caregivers review a postcard consent about the study, they will be asked to answer a question in REDCap indicating if they agree to participate. If the child is of assenting age (7-17), we will have the child review a postcard assent about the study. They will then be asked to answer a question in REDCap indicating if they agree to participate. The postcard consent/assent will describe our goal as studying child safety in general and will not specifically refer to a firearm safety objective, in order to mitigate potential bias. We will debrief the caregiver about the minor deception after they complete the follow-up survey, as knowledge of study aims could bias answers to both the baseline and follow up survey.

Specific aims 1 and 2: To prevent potential contamination across providers in the ED, the intervention will only be given during one block of time. Families will be block randomized by date of presentation. In the first six months, or until we recruit the necessary number of participants, we will provide current standard of care with no new intervention – this will be group 1 (G1). In the following six months we will recruit into the intervention group – this will be group 2 (G2). In G1, parents will complete the baseline survey at time 0 (t0) and will complete the follow-up survey at 3 months (t3) via follow up phone call. In G2, parents will be asked to complete the baseline survey at t0 and will then be asked to watch the 3-minute Be SMART video. Parents in G2 will also complete the follow-up survey at t3 via follow up phone call.

Specific aims 3, 4 and 5: Those answer yes in REDCap indicating that they agree to participation will be randomized to watch either the 30-second or 3-minute Be SMART video. Each family enrolled will be asked to watch one of these two videos.

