Continuous variables will be described as means and standard deviations if normally distributed or median and interquartile range if non-normally distributed. Categorical variables will be described using counts and percentages. We will compare data between families who received the 30-second video and the 3-minute video using fisher exact tests, t-tests, or Wilcoxon rank sum tests as appropriate. All results will be presented in aggregate and performed in SAS (Cary, NC).

H. Summarize Knowledge to be Gained:

This study has the potential to utilize a novel approach to educating the public about safe firearm storage. If successful, it can improve rates of safe firearm storage where children and adolescents are living and increase safe firearm behaviors, thereby reducing morbidity and mortality caused by suicide, unintentional injuries, and assaults.

I. References

1. Runyan, C.W., et al., *Lethal Means Counseling for Parents of Youth Seeking Emergency Care for Suicidality*. West J Emerg Med, 2016. **17**(1): p. 8-14.
2. Cunningham, R.M., M.A. Walton, and P.M. Carter, *The Major Causes of Death in Children and Adolescents in the United States*. N Engl J Med, 2018. **379**(25): p. 2468-2475.
3. National Center for Health Statistics, C.f.D.C.a.P. *Stats of the State of Colorado*. April 13, 2018 [cited Sept 9 2019]; Available from: <https://www.cdc.gov/nchs/pressroom/states/colorado/colorado.htm>.
4. Pediatric Patient Education, A.A.o.P. *Firearms Injury Prevention*. [cited 2019 September 12]; Available from: <https://patiented.solutions.aap.org/handout.aspx?gbosid=166212>.
5. Grossman, D.C., et al., *Gun storage practices and risk of youth suicide and unintentional firearm injuries*. JAMA, 2005. **293**(6): p. 707-14.
6. Simon, O.R., et al., *Characteristics of impulsive suicide attempts and attempters*. Suicide Life Threat Behav, 2001. **32**(1 Suppl): p. 49-59.
7. Elnour, A.A. and J. Harrison, *Lethality of suicide methods*. Inj Prev, 2008. **14**(1): p. 39-45.
8. Spicer, R.S. and T.R. Miller, *Suicide acts in 8 states: incidence and case fatality rates by demographics and method*. Am J Public Health, 2000. **90**(12): p. 1885-91.
9. Azrael, D., et al., *Firearm Storage in Gun-Owning Households with Children: Results of a 2015 National Survey*. J Urban Health, 2018. **95**(3): p. 295-304.

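### Aims 1 and 2 are called block randomised but compare two consecutive calendar periods, and the Data Analysis Plan names no comparison or test that uses the control group's storage and knowledge data

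*Combined protocol and SAP*

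**What the plan says.** All references are to the combined protocol and SAP.

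- **Allocation (III.C, Specific aims 1 and 2).** The label is "Families will be block randomized by date of presentation". To avoid contamination between providers, "the intervention will only be given during one block of time". In the first six months, or until enough participants are recruited, "we will provide current standard of care with no new intervention" (G1). Then: "In the following six months we will recruit into the intervention group" (G2).
- **Data collected (III.C).** G1 completes the surveys at t0 and t3. G2 completes the t0 survey and is asked to watch the 3-minute video. "Parents in G2 will also complete the follow-up survey at t3 via follow up phone call".
- **Objective (section I).** Aim 1 is assessed by "measuring change in self-reported safe storage at baseline and 3 months after a brief ED intervention". Its hypothesis is "Safe storage counselling will improve safe storage practices by 15% over baseline rates". Aim 2 is worded in a similar way for parental knowledge. Neither aim mentions a control group.
- **Analysis (III.G).** Apart from generic descriptive statistics there is one comparison: "We will compare data between families who received the 30-second video and the 3-minute video". G1, G2, a paired t0–t3 analysis and calendar period do not appear.

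**The concern.** There are two separate problems.

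**Label.** Randomisation is what lets a difference between groups be read as caused by the intervention. In this protocol the word has its ordinary meaning for aims 3–5, where caregivers are randomised to one of two videos. A reader will carry that meaning over to aims 1 and 2, where no chance mechanism is described.

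**Analysis.** A control group measured at both times is the one feature of this design that can help separate the video from other causes of change, yet no comparison or test is written for its storage and knowledge data. The aim 1 hypothesis is set against baseline rates, so an analyst could report the before-after change in G2 alone. That change mixes the video with anything else that moves the answers over three months, including being asked the same safety questions twice.

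Aims 1 and 2 set out to assess effectiveness, and their outcomes head the list of primary measures in III.A. At stake is what the trial can conclude about the video.

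**Working it through.** **1. The allocation.** There are two periods in a fixed order, one per group. Only one allocation is possible, so group and period coincide. Drawing the order by lot would not help: one block per group still cannot separate the video from the period.

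**2. Where G1's data go.**

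| G1 data | Stated use |
|---|---|
| Agreement to take part; t0 survey completion; t3 survey completion | Can feed feasibility outcomes 4a, 4c and 6 in III.A, listed under aims 1–5 |
| All variables | Can enter the generic summaries in III.G |
| Storage and knowledge at t0 and t3 | No named comparison or test |

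**3. Illustration of size.** The plan has no sample size, power or error rate to reproduce. Assumptions:

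- safe storage p = 1/3 at t0 (background figure in section II, not shown to match the aim 1 definition);
- within-family correlation ρ = 0.6, range 0.4–0.8;
- n = 50 to 250 completers per group;
- two-sided 5% test, no video effect, and a shift d of 5 points.

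Formulas:

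- P(safe at both times) = p_t0·p_t3 + ρ√[p_t0(1−p_t0)·p_t3(1−p_t3)].
- Variance of one family's change: v = P(safe→unsafe) + P(unsafe→safe) − (p_t3−p_t0)².
- Standard error: √(v_G2/n) for before-after in G2; √(v_G1/n + v_G2/n) for G2 minus G1.
- Rejection rate: Φ(−1.96 + d/se) + Φ(−1.96 − d/se).

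With ρ = 0.6:

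- No change (1/3 to 1/3): P(both) = 0.2444 and v = 2(0.3333 − 0.2444) = 0.1778.
- A 5-point rise (0.3333 to 0.3833): P(both) = 0.2653 and v = 0.0680 + 0.1180 − 0.0025, or 0.1836 before rounding of the terms.

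At n = 170:

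- Before-after in G2: se = √(0.1836/170) = 0.0329, rejection 33.1%.
- G2 minus G1, with the shift in G2 only: se = √[(0.1778 + 0.1836)/170] = 0.0461, rejection 19.2%.

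| Completers per group | Shared 5-point change: before-after in G2 | Shared 5-point change: G2 minus G1 | 5-point period difference in the change: G2 minus G1 |
|---|---|---|---|
| 50 | 13.1% | 5% | 9.0% |
| 100 | 21.5% | 5% | 13.2% |
| 170 | 33.1% | 5% | 19.2% |
| 250 | 45.4% | 5% | 26.0% |

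Over ρ = 0.4 to 0.8 and the same sizes, the before-after rate runs from 10.3% to 74.1%, and the last column from 7.7% to 46.0%.

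**4. Limit of the 5% column.** It holds because the same number of points was added in both groups. Suppose instead that the shared change is equal in odds and the groups differ at t0. A 10-point rise from 33.3% to 43.3% is an odds ratio of (0.4333/0.5667)/0.5 = 1.53. From 20% the same odds ratio gives odds of 0.25 × 1.53 = 0.382, or 27.7%. That is a rise of 7.7 points, so 2.3 points would remain in the contrast.

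**5. Cost of using change.** The interval for the change contrast, relative to one adjusted for t0 status, has width ratio √[2(1−ρ)/(1−ρ²)] = 1.195, 1.118 and 1.054 at ρ = 0.4, 0.6 and 0.8.

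**The case against.** The sequence is set out openly right after the disputed sentence, and it has a stated reason: keeping the intervention from spreading between providers. III.C opens by calling the study pre-post. Section II speaks of pilot data and leaves the evaluation of effectiveness to a later randomised trial, and III.F gives the goal as feasibility and acceptability. A careful reader would not take aims 1 and 2 for a randomised trial. All of this stands and limits the harm. But the contamination argument supports the sequence, not the label, and section I still frames both aims as tests of effectiveness.

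Three stronger readings are tempting, and the documents do not support them:

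- A reader might infer that G1 is collected for nothing. It can contribute to outcomes 4a, 4c and 6 and to the descriptive summaries. The gap is confined to storage and knowledge.
- A reader might infer that the plan commits to a before-after test in G2 alone. No such test is named. The aim 1 hypothesis allows that reading, but surveying G1 twice points towards an intended control comparison.
- A reader might infer that randomisation is absent throughout. Aims 3–5 do describe randomising caregivers to video length.

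The rejection rates are also open to challenge, since sample size, correlation and shift are all assumed and the rates are lowest at small pilot sizes. That is fair. Neither problem depends on the rates.

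**Conclusion.** Both problems hold and should be fixed. The randomisation label for aims 1 and 2 is wrong as written: the design is a non-randomised comparison of two consecutive cohorts. III.G names no comparison or test using G1's storage and knowledge data. These conclusions rest on the text alone and do not need the illustration.

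The two differ in what can be done. Using G1 removes non-video change that both groups share, provided it is equal on the risk-difference scale. A reader might infer that naming the G2-minus-G1 contrast therefore makes the result causal. It does not: a period difference in the 3-month change stays inside that contrast, and no analysis of one period per group removes it. Under the stated assumptions, a 5-point difference of that kind yields 9–26% false positives at ρ = 0.6.

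**What to change.** Text only; the t0 and t3 surveys are already planned in both groups.

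1. In III.C, replace the allocation sentence with: *Families are assigned to G1 or G2 by the calendar period in which they present; there is no randomisation. Aims 1–2 are a non-randomised sequential-cohort comparison.* The same section calls the study both experimental and observational; reconcile those terms with this sentence.
2. In III.G, add: *For each aim 1–2 outcome the main comparison is the t0-to-t3 change in G2 minus that in G1, on the risk-difference scale, with a 95% CI allowing for repeated measures within family. A model adjusting for t0 status is reported beside it, and t3 completion is reported by group.* The last item matters because the aim 5 hypothesis expects only 65% to complete follow-up.
3. Limit the aims 1–2 conclusion to association, and state calendar-time confounding as a limitation that no analysis of one period per group removes.

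The costs are a weaker stated conclusion and an interval about 12% wider than with baseline adjustment at an assumed correlation of 0.6 (about 20% at 0.4, 5% at 0.8). Change is proposed as the main comparison because aim 1 is worded as change, not because it is always less biased.
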